5.2.3 Streamlined Group (SG)

a. Video-Assisted Genetic Education

- After completion of the baseline surveys, the SG subjects will watch an approximately eight minute long genetics education video. This video will be made with the assistance of Duke University genetic counselors and gynecologic oncology providers. It will consist of a discussion of genes and mutations, the recommendation of universal testing for high grade epithelial ovarian cancer, a review of genes associated with ovarian cancer predisposition, the possibility of uncertain results including variants of undetermined significance, the potential for undetected mutations in known or unknown cancer susceptibility genes, the potential impact on personal treatment and on family members, the possibility of genetic discrimination and the legal protection of genetic information.
- After watching the video, the primary oncologic provider will then offer multi-gene panel testing.
- All subjects will then have the option to "opt out" and receive formal genetic counseling prior to making a decision about testing.
- If the subject elects to undergo genetic testing, she will fill out the standard genetic testing consent form. As per standard practice of the clinical genetic service at DCI, patients will also be asked to provide consent for somatic tumor testing of surgical specimen (non-cytologic).

b. Electronic Family History Questionnaire

- SG subjects will complete an electronic family history questionnaire (FHQ) within one week of the primary visit. This is a system already employed by the Duke Clinical Genetics Department. An email is sent to the subject's primary email account with a link to a secure, HIPAA compliant portal, in which the subject can then enter her family cancer history.
- A member of the genetics team will curate the results by contacting the subject to review common errors and clarify any ambiguities in the pedigree.

c. Post-education distress measurement

- Subjects will complete a post-education distress and anxiety survey (IES) via an email link to a confidential REDCap survey link within one week of formal consultation.

5.2.3 Results Disclosure (Both groups)

- Subjects will be notified of their results by the genetic counselor over the phone and triaged accordingly.
 - Deleterious mutation, VUS or high-risk family history despite negative genetic testing results: Scheduled for formal post-testing consultation 2-4 weeks after result return
 - No deleterious mutation or VUS identified on genetic testing and low risk family history: No further genetics follow-up needed

5.2.4 Follow-up

- All subjects will take a satisfaction with genetic counseling survey (MICRA) after receiving results approximately seven days after either formal consultation or reception of results over the phone [25]. The survey will be sent via email via a confidential REDCap survey link.

5.3 Outcome Variables

5.3.1 Demographic information

Measurement time: Baseline

Description: Demographic information, including cancer history, age, race, marital status, and income will be collected from each participant upon enrollment.

5.3.2 Numeracy assessment

Measurement time: Baseline

Description: Numeracy and health literacy will be assessed using the Newest Vital Sign survey, a six-question survey that asks questions about a provided ice cream nutrition label [26].

5.3.3 Electronic family history

Measurement time: A secure email sent to patient immediately after first visit; completed at home within one week of visit

Description: This is a system already employed by the Duke Clinical Genetics Department. An email is sent to the subject's primary email account with a link to a secure, HIPAA compliant portal, in which the subject can then enter her family cancer history for three generations. A member of the genetics team will curate these results.

5.3.4 Anxiety and depression

Measurement time: Baseline, post-education and post-results disclosure

Description: The Impact of Events Scale (IES) has been used widely as a means of measuring patient distress (particularly intrusive thoughts or avoidance) over a defined incident [27]. This evaluation will be used to identify trends in anxiety or depression in both arms throughout the education and testing process. In this trial, the "incident" will be described as "the risk of my cancer being hereditary."

5.3.5 Distress

Measurement time: Post-results disclosure

Description: The multidimensional impact of cancer risk assessment questionnaire (MICRA) is a 25-question validated tool that measures the impact of result disclosure in patients, particularly markers of distress [25].

5.3.6 Resource utilization

We will evaluate the cost of physician, genetic counselor and genetic assistant time based on average base wages for these positions and total mean time spent by each of these providers. These estimates will be obtained for approximately forty patients –twenty from each arm – enrolled mid-trial to ensure that the process time in the streamlined group has reached full efficiency. Each provider will record time for each of these parameters using a stopwatch, with total times entered into the REDCap database.

Times measured in both arms will include:

Family History Curation

- GC phone time

- GC documentation or computer entry

- Staff phone time

Staff documentation or computer entry

Pre test counseling (Any time prior to results disclosure)

GC phone time

GC documentation or computer entry

GC face-to-face counseling

Staff phone time

Staff documentation or computer entry

Post test (From time of results disclosure on)

GC results disclosure phone time

GC face-to-face counseling

GC other phone time (not including results disclosure)

GC documentation or computer entry

Staff phone time

Staff documentation or computer entry

We will evaluate the cost of physician, genetic counselor and genetic assistant time based on average base wages for these positions and total mean time spent by each of these providers.

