5.2 Study Procedures (See Figure One)

5.2.1 *Baseline Questionnaires (Both Groups)*

- After randomization, each subject will complete a series of baseline questionnaires on a tablet in the gynecologic oncology clinic, entering their results directly into the secure REDCap database. These baseline questionnaires include a basic numeracy test, the baseline anxiety and distress survey (IES) and the demographic information questionnaire, which will include questions concerning age, race, marital status, home address, and income [26,27].

5.2.2 *Tradition Counseling Group (TG)*

a. Formal Consultation Scheduling

- After completion of baseline surveys, the TG subjects will be referred to a formal pre-test consultation with a genetic counselor that will be scheduled for a date approximately 2-4 weeks after their primary appointment (for patients in whom results will determine treatment, appointments will likely be expedited). They will be made aware of the date and time of this appointment prior to leaving their initial visit.

b. Electronic Family History Questionnaire

- TG subjects will complete an electronic family history questionnaire (FHQ) within one week of the primary visit. This is a system already employed by the Duke Clinical Genetics Department. An email is sent to the subject's primary email account with a link to a secure, HIPAA compliant portal, in which the subject can then enter her family cancer history.
- A member of the genetics team will curate the results by contacting the subject to review common errors and clarify any ambiguities in the pedigree.

c. Formal Consultation and Post-Counseling Distress Survey

- The TG subjects will then meet with the genetic counselor at the previously scheduled appointment time. During this visit, they will receive approximately thirty to sixty minutes of counseling regarding genetic testing and potential results. The discussion is based on the ASCO and NCCN guidelines of informed consent for genetic testing.
- After counseling, participants will be given the option to undergo a multi-gene panel genetic test either via saliva or blood sample. Those who agree to testing will also complete the standard genetic testing consent form. As per standard practice of the clinical genetic service at DCI, patients will also be asked to provide consent for somatic tumor testing of surgical specimen (non-cytologic).

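### Section 5.3.6 promises to cost physician time, but none of its 15 listed time items belongs to a physician, so the streamlined arm's provider offer of testing has no field

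*Combined protocol and SAP*

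**What the plan says.** Section 5.3.6 (Resource utilization) sets out the cost method: "We will evaluate the cost of physician, genetic counselor and genetic assistant time based on average base wages for these positions", combined with the mean total time of each position. The statement appears twice, before and after the list of times. Timing is done in about forty patients, twenty per arm, enrolled mid-trial. On recording: "Each provider will record time for each of these parameters using a stopwatch, with total times entered into the REDCap database". The list opens with "Times measured in both arms will include" and has three blocks: family history curation, a pre-test block headed "Pre test counseling (Any time prior to results disclosure)", and a post-test block. Every item is labelled either GC or Staff, and Staff is not defined.

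The arms differ in who brings the patient to the testing decision. For TG, section 5.2.2 says of the counsellor visit: "During this visit, they will receive approximately thirty to sixty minutes of counseling regarding genetic testing and potential results", and then: "After counseling, participants will be given the option to undergo a multi-gene panel genetic test either via saliva or blood sample". For SG, section 5.2.3 (Streamlined Group) says: "After watching the video, the primary oncologic provider will then offer multi-gene panel testing".

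The time data serve secondary objective (a) in section 2, whose hypothesis is that the streamlined model is the cheaper one. Section 5.4.3 plans only a comparison of means by summary statistics.

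**The concern.** The section commits to costing three positions but lists times for at most two. The missing position matters because the streamlined model moves the offer of testing out of the counsellor's session and into the oncology visit. A list with counsellor items and no provider items records the work removed from TG practice but not the provider work that partly takes its place.

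At stake is the cost comparison in secondary objective (a). If provider time is left out, SG will look cheaper than it is whenever SG uses more provider time than TG, which is the direction of the stated hypothesis. Nothing else in the documents would fill the gap. Section 5.4.3 names no other source of physician time. Billing is no obvious substitute, because section 4.3.3 says that neither form of pre-test education is billed at the lead site. Minutes not timed during a visit cannot be measured afterwards for that patient.

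**Working it through.** The plan states no figure to reproduce here, so the check is a count, a comparison of the arms and an illustrative break-even.

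**1. Items in section 5.3.6, by block and role**

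| Block | GC | Staff | Physician or other oncology provider | Total |
|---|---|---|---|---|
| Family history curation | 2 | 2 | 0 | 4 |
| Pre-test | 3 | 2 | 0 | 5 |
| Post-test | 4 | 2 | 0 | 6 |
| All | 9 | 6 | 0 | 15 |

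**2. The same items by type**

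- Phone: 4 GC + 3 Staff = 7
- Documentation or computer entry: 3 GC + 3 Staff = 6
- Face-to-face: 2 GC + 0 Staff = 2
- Total: 7 + 6 + 2 = 15

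So 1 of the 3 costed positions has 0 of 15 items, 0 of the 5 pre-test items and 0 of the 2 face-to-face items.

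**3. Matching the steps to the items**

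- TG: the 30 to 60 minute counsellor session falls under the pre-test GC face-to-face item, so it is timed.
- SG: the provider's offer of testing after the video is a clinic-visit activity by someone who is not a counsellor. The Staff items cover only phone and documentation, so no item fits.
- TG clinic work: subjects are referred at the first visit, and "They will be made aware of the date and time of this appointment prior to leaving their initial visit". Any physician time spent on this is also unlisted.

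**4. Form of the error**

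Let w be the provider wage per minute, and m_SG and m_TG the mean provider minutes per patient on genetic testing in each arm. If provider time is not recorded, the SG-minus-TG cost difference omits

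w × (m_SG − m_TG).

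SG is understated relative to TG when m_SG exceeds m_TG. The documents give none of these three quantities.

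**5. Break-even, under assumptions that are not in the documents**

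Assume the physician wage is r times the counsellor wage, with r from 2 to 4, and that SG saves the whole TG session of T minutes. The session's cost is fully offset when net provider minutes equal T / r:

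- T = 30: 30/4 = 7.5 and 30/2 = 15 minutes
- T = 60: 60/4 = 15 and 60/2 = 30 minutes

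The range is 7.5 to 30 net provider minutes; fewer minutes offset the session only in part. This shows what provider time would matter. It does not estimate the bias.

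**The case against.** The best reply is that the list is not closed. Its lead-in says only what the times will include, physicians are among the named providers, and each provider is told to record time. The REDCap form itself is not in the documents. On this reading an item label is missing, not a measurement. The reply is fair as far as it goes, and it is why the consequence is stated conditionally. But the recording instruction is tied to the listed parameters, and none of them is a physician's.

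Staff might also be read to mean everyone who is not a counsellor. That would give provider documentation a field. It would still leave no face-to-face field, and it would pool physicians with assistants, so the separate wages that the section calls for could not be applied.

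The direction of bias is an inference. The education in SG comes from a video of about eight minutes, the only provider task named is the offer of testing, and TG clinic time is unlisted too. This stands: the direction is probable, not shown.

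The break-even also has limits. The wage ratio is assumed. The SG option to have formal counselling first would reduce the counsellor time saved and lower the break-even. Savings in pre-test counsellor phone and documentation time would raise it. It should not be read as the size of the problem.

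Finally, timing covers about 40 of up to 112 patients, so a gap noticed during accrual could be repaired by timing later enrollees. That is true for the trial, but not for patients already seen.

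**Conclusion.** The concern holds. Section 5.3.6 is inconsistent with itself: physician time is to be costed, yet 0 of 15 items collect it and no other section supplies it. That part rests on a count and is certain.

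The effect on the cost comparison depends on recording following the list. If it does, SG cost is understated relative to TG by the provider wage times the net provider minutes, probably in favour of the hypothesis. The size cannot be estimated from the documents.

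The scope is limited to secondary objective (a), a descriptive comparison in about 40 patients. The primary MICRA endpoint is unaffected. The plan should be corrected, because without the correction the cost comparison may omit one of the three inputs it says it will use.

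**What to change.** In section 5.3.6, for both arms:

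1. Add two pre-test items for the oncology provider: face-to-face time on genetic testing, and documentation or ordering time. Record the provider's role (physician or APP) with each.
2. Define Staff as distinct from physicians, for example as the genetic assistant, so that the right wage is applied to each item.
3. State, here and in section 5.4.3, that provider time multiplied by the provider wage enters the between-arm cost comparison.
4. Have the fields working before the mid-trial timing sample begins.

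The list grows from 15 to 17 items. The added recording is 2 fields × about 40 patients = about 80 time entries, about 40 per arm, plus a role code. If APPs make some of the offers, one further wage figure is needed. The drawback is a small recording burden on clinic providers during visits. Sample size, primary analysis and patient procedures do not change.

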5.4 Statistical Methods

5.4.1 Demographic and Baseline Survey Information

The SG and TG will be compared at baseline regarding demographic information, medical and family history and baseline distress as measured by the Impact of Events Scale. Categorical variables will be tested using the Chi-Square test. Continuous variables will be assessed using the Student T test or the Mann-Whitney U test for non-normal data. Equality of variance across these variables will be assessed. Any variables with a significant difference greater than $p=0.1$ will be controlled for in future analyses.

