5.1 Randomization

Following consent, the clinical research coordinator will randomize the patient to either the Traditional Group (TG) or Streamlined Group (SG). The randomization process will have occurred previously using the REDCap randomization tool.

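### Family history is listed as a baseline variable that may be adjusted for, but its only scheduled measurement comes after randomisation: after education in the streamlined arm and normally before it in the traditional arm (minor).

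*Combined protocol and SAP*

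**What the plan says.** **Analysis.** Section 5.4.1 sets out the baseline comparison: "The SG and TG will be compared at baseline regarding demographic information, medical and family history and baseline distress". It then says that variables flagged at a threshold of p = 0.1 "will be controlled for in future analyses". I read the threshold as p below 0.1. The section names no source for family history and does not say which later analyses the rule covers. Section 5.4.2 specifies a two-sample one-sided t-test on MICRA, without covariates. Section 5.4.3 compares testing uptake by logistic regression.

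**Randomisation and baseline surveys.** Section 5.1: "Following consent, the clinical research coordinator will randomize the patient". Section 5.2.1 then lists the tablet surveys: "These baseline questionnaires include a basic numeracy test, the baseline anxiety and distress survey (IES) and the demographic information questionnaire". Family history is not among them.

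**Family history.** Section 5.3.3 gives the timing of the three-generation questionnaire: "A secure email sent to patient immediately after first visit; completed at home within one week of visit". The arm-specific sections agree. For the traditional group (5.2.2): "TG subjects will complete an electronic family history questionnaire (FHQ) within one week of the primary visit". For the streamlined group (5.2.3): "SG subjects will complete an electronic family history questionnaire (FHQ) within one week of the primary visit". In both arms genetics staff then contact the woman to clean up the pedigree; no time limit is given.

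**Education.** Section 5.2.3: "After completion of the baseline surveys, the SG subjects will watch an approximately eight minute long genetics education video". The testing offer follows the video. In the traditional arm, 5.2.2 places counseling about 2 to 4 weeks after the primary visit, sooner where results will determine treatment.

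**The concern.** A covariate used to adjust a randomised comparison should not be open to influence by the arm. A woman's true family history is settled before she is randomised, but the analysis would use what she reports and what staff then curate. A streamlined-arm woman answers after a video that covers cancer predisposition genes and the effect on relatives. A traditional-arm woman usually answers before her counseling. If education changes which relatives and cancers she looks up and reports, a difference between arms may be an effect of the arm rather than a chance imbalance.

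The rule in 5.4.1 makes this awkward because it adjusts only when the arms differ, so it would bring the variable in just when differential reporting had occurred. If streamlined women reported more history, and reported history went with higher MICRA, adjustment would lower the streamlined-minus-traditional estimate and make non-inferiority easier to claim. For uptake, a streamlined woman who decides about testing at the visit would have the covariate measured after the outcome.

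**Working it through.** **1. Order of events** (5.1, 5.2.1 to 5.2.3, 5.3.3)

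| | Streamlined | Traditional |
|---|---|---|
| Day 0 | Randomisation, tablet surveys, video, testing offer | Randomisation, tablet surveys |
| To day 7 | FHQ | FHQ |
| About day 14 to 28 | – | Counseling (earlier if expedited) |

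The testing offer on day 0 is implied by the sequence in 5.2.3, not dated. Expedited counseling has no minimum interval, so a few traditional-arm women could be counseled before they return the FHQ.

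**2. The plan's own figure.** Inputs from 5.4.2: margin 4.2, SD 8.4, true difference 0, one-sided 0.05, power 80%. Per arm, n = 2 × (1.645 + 0.842)² × (8.4/4.2)² = 49.5, so 50. The exact t-test gives power of 79.9% with 50 per arm and 80.6% with 51. The stated 51 per arm is reproduced, and nothing in this point changes it.

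**3. Size if the rule is applied to MICRA.** The documents give no prevalence of reported history, no effect of the video on reporting and no link to MICRA. All three are assumed here: 30% reporting in the traditional arm; 10, 15 or 20 percentage points more in the streamlined arm; reported history worth 4.2 MICRA points (0.5 SD).

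- Chance of being flagged, 15 points, 51 per arm: SE = √(0.30 × 0.70/51 + 0.45 × 0.55/51) = 0.0947; z = 0.15/0.0947 = 1.58; P(p < 0.1) = 0.48. With 56 per arm (112/2) it is 0.51.
- Shift in the adjusted estimate: 0.15 × 4.2 = 0.63 points, which is 0.63/4.2 = 15% of the margin.
- SE of the MICRA difference: 8.4 × √(2/51) = 1.66.
- False non-inferiority with the true difference at the margin, if history were **always** adjusted for: 1 − Φ(1.645 − 0.63/1.66) = 0.103. For 10 and 20 points: 0.082 and 0.127.

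Section 5.4.1 adjusts only if the variable is flagged. I simulated that two-step rule: 51 per arm, total SD 8.4, true difference at 4.2, adjusted analysis if the family history test gives p < 0.1 and the unadjusted t-test otherwise.

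| Added reporting | MICRA points for reported history | Always adjusted | Adjusted only if flagged |
|---|---|---|---|
| 10 points | 4.2 | 8.2% | about 6.5% |
| 15 points | 4.2 | 10.3% | about 8% |
| 20 points | 4.2 | 12.7% | about 11% |
| 5 points | 2.1 | 5.7% | about 5% |

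These figures let the extra reporters carry the full 4.2 points. If the video changes only what is reported, so that the extra reporters are no more distressed than other women, the pooled slope weakens. At 15 points the shift is then about 0.51 rather than 0.63, and the flagged-only rate is between 7% and 8%.

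**The case against.** The strongest reply is that the primary analysis does not use family history. Section 5.4.2 specifies an unadjusted t-test, and no adjusted MICRA model is described anywhere. Bias therefore needs two steps: the 5.4.1 rule must be taken to reach MICRA, and family history must be flagged. This stands, and it limits the point. It does not remove it, because 5.4.1 speaks of later analyses in general and exempts none.

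Second, the arms share the same questionnaire, the same one-week window and the same curation, which should narrow reporting differences. Traditional-arm women also answer knowing that a genetics appointment is booked, which may itself prompt recall. The described video content does not include instruction on taking a family history. All this makes a large reporting effect less likely, though it does not turn the streamlined-arm measurement into a baseline one.

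Third, 5.4.1 does not name the FHQ, so chart data might be meant. Section 5.3.1 does list cancer history among the baseline demographics, and eligibility screens for a known familial mutation. Neither is a family pedigree, and no other family history measurement is scheduled. The ambiguity is itself a reason to name the source.

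A reader might go further and infer that the primary test has a false-positive rate of about 10%, or 8 to 13%. The documents do not support that: those figures assume adjustment every time and a video effect that nobody has measured. Nor do they support a claim that the bias must favour the streamlined arm. If education reduced reporting, or reported history went with lower MICRA, the sign would reverse. Finally, the plan gives no adjusted model and no missing-data rule for one, so it cannot be said that women who fail to return the FHQ would be dropped.

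**Conclusion.** The timing problem holds on the text: a variable called baseline is collected after randomisation, on opposite sides of the education step in the two arms, and a stated rule can bring it into the comparison. The consequence is conditional. It arises only if that rule is applied to MICRA or to the uptake regression, and only if education changes what women report.

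The documents fix neither direction nor size. Under the assumed 10 to 20 points of added reporting and a 4.2-point association, the rule as I read it gives about 6 to 11% false non-inferiority against 5%; under 5 points and a slope of 2.1 it stays at about 5%. The sample size and the unadjusted primary test are unaffected. I rate the point minor, and worth making because the correction is so cheap.

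**What to change.** In 5.4.1, take FHQ-derived family history out of both the baseline tests and the set of variables that may be controlled for. Suggested wording:

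> Family history from the electronic questionnaire is obtained after randomisation. It will be summarised by arm, with completion rates, and will be neither tested as a baseline characteristic nor used as an adjustment covariate.

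If a baseline family history factor is wanted, define it from the medical record as it stood before randomisation, or add one short tablet item on affected first-degree relatives, completed before the video. The tablet surveys follow randomisation under 5.2.1, so such an item would be pre-education rather than strictly pre-randomisation; the chart variable avoids this.

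The cost is one sentence, plus a chart variable or one item if chosen. No visit or sample size changes. The downside is a coarser measure than the curated pedigree, which remains available for triage and description.

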5.4.2 Primary endpoint

The study is powered as a non-inferiority analysis of distress associated with streamlined genetic education and testing versus traditional pre-test genetic counseling and testing.

A two sample one-sided t-test is used to check the non-inferiority for the experimental treatment in terms of the MICRA (Multidimensional Cancer Risk Assessment questionnaire). We assumed the mean MICRA scores for both experimental arm and control arm will be the same and equal to 13.5, with a common standard deviation of 8.4. These values were obtained from a study that assessed the MICRA in a similar patient population [25]. Using these estimates, a total sample size of 102 (51 patients each arm) will provide 80% power to detect the non-inferiority for the experimental treatment with a significance level of 0.05 and a non-inferiority margin of 4.2 (50% standard deviation). This margin was chosen as a high general MICRA score has previously been considered to be one standard of deviation above the mean; thus, we are taking a more conservative approach by using a non-inferiority margin of 0.5 the expected standard deviation observed in Cella et al [28]. When incorporating a potential 10% attrition rate, the total sample size will be 112.

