5.4.3 Secondary endpoints

Resource utilization

Mean resource utilization will also be compared between the two models using summary statistics.

Genetic testing uptake

Genetic testing uptake between the two groups will be compared using logistic regression.

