5.4.4 Exploratory endpoints

Impact of Events Scale

Mean changes in the Impact of Events Scale scores between each administration point will be compared between the two arms using the Wilcoxon rank sums test.

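### The covariate rule in section 5.4.1 is worded backwards, lets chance baseline differences pick the covariates, and does not say whether it applies to the primary t-test

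*Combined protocol and SAP*

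**What the plan says.** Section 5.4.1 sets out a comparison of the two arms on demographics, personal and family medical history, and a distress score, described as "baseline distress as measured by the Impact of Events Scale" (IES). Chi-square, t or Mann-Whitney tests are to be used. The section ends with the plan's only covariate rule: "Any variables with a significant difference greater than $p=0.1$ will be controlled for in future analyses".

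The sections that follow name these analyses:

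- Section 5.4.2, primary endpoint: "A two sample one-sided t-test is used to check the non-inferiority for the experimental treatment in terms of the MICRA". No covariates are named and there is no reference back to 5.4.1.
- Section 5.4.3, uptake: "Genetic testing uptake between the two groups will be compared using logistic regression". No covariates are named.
- Section 5.4.4, changes in IES: these "will be compared between the two arms using the Wilcoxon rank sums test".

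On timing, section 5.2.1 states: "After randomization, each subject will complete a series of baseline questionnaires on a tablet in the gynecologic oncology clinic". MICRA is measured only after results disclosure (section 5.3.5), so it has no baseline value. Baseline IES is the closest measure available.

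**The concern.** There are three separate faults.

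1. **Direction.** A difference with p above 0.1 is the absence of a notable imbalance. As written, the rule adjusts for those variables and omits the imbalanced ones.
2. **Selection by chance.** In a randomised trial, baseline differences between arms arise by chance. A p < 0.1 screen would admit any given variable about one time in ten, whether or not it predicts MICRA. What makes a covariate worth adjusting for is its relation to the outcome, and the screen does not look at that.
3. **Scope.** The rule is said to cover later analyses without naming them. Neither the two-sample t-test nor the Wilcoxon test can take a covariate; of the tests named, only the logistic regression can. So the rule may apply to uptake alone, or it may replace the primary t-test with an adjusted model.

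The non-inferiority conclusion rests on one upper confidence bound against 4.2. If the plan does not fix whether that bound is adjusted, two analysts following it could reach different conclusions from the same data.

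**Working it through.** **Inputs from section 5.4.2:** 51 per arm, SD 8.4, margin 4.2, one-sided alpha 0.05, and the planning assumption that "the mean MICRA scores for both experimental arm and control arm will be the same and equal to 13.5", so the true difference is 0. **Assumed, not in the documents:** the correlation r between baseline IES and MICRA, taken as 0.3 and 0.5, with 0 and 0.1 as checks.

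**Step 1. The plan's own figure.** SE = 8.4 × √(2/51) = 1.663. Noncentrality = 4.2 / 1.663 = 2.525. With 100 df the critical value is 1.660 and the noncentral-t power is 80.6%. The stated 80% with 51 per arm is reproduced, for an unadjusted t-test.

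**Step 2. How often chance selects covariates.** With k independent candidates, P(at least one has p < 0.1) = 1 − 0.9^k. This is 10% for one variable, 47% for 6, 57% for 8 and 65% for 10. The plan does not fix k.

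**Step 3. What a fixed adjustment is worth.** Residual SD = 8.4 × √(1 − r²), which is 8.01 at r = 0.3 and 7.27 at r = 0.5. The noncentrality is 2.647 and 2.915, and on 99 df the power is 83.7% and 89.4%. Simulated values (step 4) are slightly lower because chance imbalance in the covariate widens the standard error.

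**Step 4. Simulation of the possible readings.** 200,000 trials per setting, IES and MICRA bivariate normal, IES the only covariate. Type I error is taken at a true difference of 4.2 and power at 0. The Monte Carlo standard error is about 0.05 points at 5%. Entries are for r = 0.3 / r = 0.5.

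| Analysis | Type I error | Power |
|---|---|---|
| Plain t-test | 5.0% / 5.0% | 80.6% |
| Adjust if p > 0.1 (literal) | 5.3% / 5.7% | about 83% / 87.5% |
| Adjust if p < 0.1 (probably intended) | 4.7% / 4.3% | 81.2% / 82.2% |
| Always adjust for IES | 5.0% / 5.0% | 83.5% / 89.1% |
| Better of adjusted and unadjusted | 6.3% / 7.0% | not relevant |

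With r = 0.1, always adjusting gives 80.7% power. With r = 0 it gives 80.2%, a cost of about 0.4 points.

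**Step 5. How often the choice changes the conclusion (true difference 0).**

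- Plain t-test against always adjusting: 6.8% / 11.9% of trials.
- Plain t-test against the literal rule: about 5% / 9%.
- Plain t-test against the p < 0.1 rule: 1.7% / 2.7%.

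**Step 6. Behaviour when IES is imbalanced.** In the 5% of trials where IES is imbalanced at p < 0.1 in favour of the streamlined group, the t-test and the literal rule both have a type I error of about 14% / 23%; always adjusting stays at about 5%. In the mirror 5%, favouring the traditional group, the t-test's error falls to about 1% or less. The two tails offset, which is why its overall rate is 5.0%.

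**Step 7. More covariates.** A separate simulation (40,000 trials per setting) with 1 or 8 candidates and r up to 0.7 gave 4.9% to 7.1% for the literal rule and 3.4% to 5.2% for p < 0.1. Reporting the most favourable of the unadjusted, p < 0.1 and p > 0.1 results gave up to 7.7% for r up to 0.5, and 8% to 9.6% at r = 0.7.

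**The case against.** The strongest reply has four parts.

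- **The slip is obvious.** The sentence speaks of a significant difference, so only p < 0.1 makes sense, and error rates for the literal rule describe an analysis nobody is likely to run. This is probably right about intent. The literal text is still the only text, and correcting the sign leaves the other two faults.
- **The primary test is named.** Section 5.4.2 specifies a t-test and the sample size reproduces for it, so the natural reading leaves it unadjusted. That is a fair reading, but 5.4.1 claims later analyses without exception. Between the t-test and the p < 0.1 rule the conclusions differ in only 1.7% / 2.7% of trials, so the ambiguity between the two likeliest readings is small.
- **Error is controlled under both likely readings.** True: 5.0%, or 4.7% / 4.3%. The 6% to 7% figures need a choice made after the results are seen. The 14% / 23% figure is conditional, has a mirror tail, and would hold for any unadjusted randomised comparison.
- **The precision gain is a preference and depends on an assumed r.** The t-test already meets the 80% target. IES here concerns the risk of the cancer being hereditary, asked before education, while MICRA concerns the impact of results, so r could be low. At r = 0.1 the gain is nil. The literal rule also keeps most of the precision; the loss belongs to the t-test and the p < 0.1 screen.

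These points limit the size of the problem. They do not remove the reversed wording, the chance selection or the open scope.

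**Conclusion.** The concern holds and should be fixed. The rule is reversed as written, chooses covariates by chance in either direction, and leaves open whether the primary bound is adjusted. Once one reading is fixed in advance, type I error stays within about 0.7 points of 5% for r of 0.3 to 0.5 with IES alone; larger departures need stronger or more numerous covariates, or a free choice between results. The main cost is unused precision. Against the p < 0.1 rule, a fixed adjustment for IES gains 83.5 − 81.2 = 2.3 points of power at r = 0.3 and 89.1 − 82.2 = 6.9 points at r = 0.5. These sizes rest on the assumed r and on normal data; the three textual faults do not. The planned sample size of 102 evaluable and 112 enrolled is not in question here.

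**What to change.** - **Section 5.4.1:** delete the p = 0.1 sentence and the baseline significance tests. Write: *Baseline characteristics will be summarised by arm; covariates will not be chosen from baseline comparisons.*
- **Section 5.4.2:** write: *The primary analysis is an ANCOVA of the MICRA score on arm with baseline IES as a fixed covariate. Non-inferiority is declared if the upper one-sided 95% confidence bound of the adjusted SG − TG difference is below 4.2. The unadjusted two-sample t-test is a sensitivity analysis. A missing baseline IES is replaced by the mean of all observed baseline values, both arms pooled.*
- **Section 5.2.1:** because the baseline IES follows randomisation, state that it is completed before the patient is told her arm, so that knowledge of the arm cannot affect the covariate.

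The cost is SAP wording and the order of one clinic step, with no new data and no change to 102/112. The downsides are a simple imputation for a missing baseline IES and about 0.4 points of power if IES and MICRA were unrelated. If the sponsor prefers the t-test as primary, deleting the rule and stating that the test is unadjusted would remove the ambiguity but forgo the precision.
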